10.1.2.1 Full Analysis Set (FAS)

For the phase 2 part of the study, the FAS includes all subjects who are treated with blinatumomab.

For the phase 3 part of the study, the FAS Includes all subjects who are randomized. Analysis will be performed according to the randomized treatment, regardless of the treatment actually received.

10.1.2.2 AutoHSCT Analysis Set

Includes all subjects who achieve a response and undergo autoHSCT.

10.1.2.3 Responder Analysis Set

Includes all subjects who had CMR or PMR after first cycle of blinatumomab or IC chemotherapy.

10.1.2.4 Safety Analysis Set

Includes all subjects from both phases of the study who received protocol-specified therapy. Analysis will be performed according to the treatment received.

With:

The primary analysis of efficacy from **the phase 2 part of the study will be performed on all subjects who received blinatumomab. The primary analysis of efficacy from the phase 3 part of the study will be performed on all randomized subjects analyzed according to their randomized treatment assignment (the Full Analysis Set [FAS]).** Sensitivity analyses of efficacy will be performed on the Safety Analysis Set.

The primary analysis of safety will be performed on the Safety Analysis Set which will include all subjects who received protocol-specified therapy analyzed according to the treatment they received.

10.1.2.1 AutoHSCT Analysis Set

Includes all subjects who achieve a response and undergo autoHSCT **while in remission and without any other anti-cancer treatment.**

Approved

10.1.2.2 Full Analysis Set (FAS)

For the phase 2 part of the study, the FAS includes all subjects who are treated with blinatumomab.

For the phase 3 part of the study, the FAS Includes all subjects who are randomized. Analysis will be performed according to the randomized treatment, regardless of the treatment actually received.

10.1.2.3 Target Dose Analysis Set (TDAS)

All subjects of the FAS who completed at least 7 days of infusion on the highest intended dose level will constitute Target Dose Analysis set (TDAS). In addition, all subjects who discontinue the treatment due to progression of disease during the first cycle of treatment will be included. The primary efficacy endpoint will be analyzed using TDAS.

10.1.2.4 Responder Analysis Set

Includes all subjects who had CMR or PMR **during the first 12 weeks** after initiation of blinatumomab or IC chemotherapy **(for phase 3)**.

10.1.2.5 Safety Analysis Set

Includes all subjects from both phases of the study who received protocol-specified therapy. Analysis will be performed according to the treatment received.

[Section 10.1.3 Covariates and Subgroups](#)

Add:

The analysis to determine if blinatumomab is superior to IC arm with respect to the primary endpoint and key secondary endpoint **for phase 3** will be stratified by the stratification factors at randomization:

- Response to S1: PMR vs NMR/PMD
- Cytarabine administered in S1 (eg, R-DHAP and R-ESHAP vs R-ICE and R-GDP): yes vs no
- PMBCL and B-cell lymphoma, unclassifiable, with features intermediate between DLBCL and classical Hodgkin lymphoma vs all other histologies of aggressive B-cell lymphoma

[Section: 10.2 Sample Size Considerations](#)

Replace:

10.2.1 Phase 2

The sample size for the phase 2 part of the study is determined by a 1-sample test of the rate of CMR after 1 cycle of blinatumomab. With the 1-sided type I error rate (α) set at 0.025, a null hypothesis response probability (π_0) of 15%, and an alternative response probability (π_1) of 40%, a sample size of 36 subjects will provide 90% power to reject the null hypothesis that the response probability is no more than 15%. Being able to make this determination will represent evidence of clinical activity and warrant advancement into the phase 3 part of the study.

With:

The sample size for the phase 2 part of the study is determined by a 1-sample test of the rate of CMR **during the first 12 weeks** after **initiation** of blinatumomab. With the 1-sided type I error rate (α) set at 0.025, a null hypothesis response probability (π_0) of 15%, and an alternative response probability (π_1) of 40%, a sample size of 36 subjects will provide 90% power to reject the null hypothesis that the response probability is no more than 15%. Being able to make this determination will represent evidence of clinical activity and warrant advancement into the phase 3 part of the study.

[Section: 10.4.4 Final Analysis](#), paragraph 2

Add:

The final analysis will test whether OS is superior in the group randomized to blinatumomab compared to the group randomized to IC. The final analysis will be triggered by the date when the 236th death in phase 3 subjects is reported in the clinical trial database, or the study duration reaches 12 months from the last subject randomized. The estimated time is 26 months to reach the OS event goal. Barring a sample-size increase, since the enrollment period is expected to last 21 months, the estimated maximum follow up time is 33 months.

In case that the phase 3 portion of the study is not initiated, the final analysis will occur when all subjects in phase 2 complete long term follow-up defined in Section 7.2.7.

[Section: 10.5.2 Primary Efficacy Endpoint](#), paragraph 1

Replace:

Phase 2:

The percentage of subjects with a CMR after the first cycle of blinatumomab will be summarized with an exact binomial 95% confidence interval. Summary of CMR during the treatment will also be provided.

With:

Phase 2:

The percentage of subjects with a CMR **during the first 12 weeks** after **initiation** of blinatumomab will be summarized with an exact binomial 95% confidence interval. Summary of CMR during the treatment will also be provided.

[Section: 10.5.3 Secondary Efficacy Endpoint\(s\), phase 2](#)

Replace:

Phase 2:

Other secondary efficacy endpoints include ORR after the first cycle of blinatumomab or IC chemotherapy and during the treatment, PFS, duration of CMR, DOR, successful mobilization rate, alloHSCT rate, autoHSCT rate and 100-day NRM after autoHSCT.

ORR after the first cycle starting blinatumomab during the treatment will be summarized with an exact binomial 95% confidence interval.

PFS will be summarized with the KM summaries.

Duration of CMR and duration of response will be summarized with the KM summaries in Responders Analysis Set.

Successful mobilization rate, autoHSCT rate and alloHSCT rate will be summarized with an exact binomial 95% confidence interval. AutoHSCT rate will be analyzed using autoHSCT Analysis Set.

The 100-day NRM after autoHSCT rate will be summarized with the cumulative incidence function with non-relapse deaths treated as competing risks. For this endpoint, time to non-relapse deaths will be measured starting from the date of autologous HSCT.

Approved

With:

Phase 2:

Other secondary efficacy endpoints include OR after **initiation** of blinatumomab and during the treatment, PFS, duration of CMR, DOR, successful mobilization rate, alloHSCT rate, autoHSCT rate and 100-day NRM after autoHSCT.

OR during the first 12 weeks after initiation of blinatumomab during the treatment will be summarized with an exact binomial 95% confidence interval.

PFS will be summarized with the KM summaries.

Duration of CMR and duration of response will be summarized with the KM summaries in Responders Analysis Set.

Successful mobilization rate, autoHSCT rate and alloHSCT rate will be summarized with an exact binomial 95% confidence interval. AutoHSCT rate will be analyzed using autoHSCT Analysis Set.

The 100-day NRM after autoHSCT rate will be summarized with the cumulative incidence function with **relapse or deaths due to relapse** treated as competing risks. For this endpoint, time to non-relapse deaths will be measured starting from the date of autologous HSCT.

[Section: 10.5.3 Secondary Efficacy Endpoint\(s\), phase 3](#), paragraph 2

Delete:

Other secondary efficacy endpoints include ORR, PFS, duration of CMR and ORR, successful mobilization rate, HSCT rate, 100-day NRM after HSCT rate. Overall response rate will be summarized by treatment group with an exact binomial 95% confidence interval.

[Section: 10.5.4.1 Adverse Events](#), paragraph 4

Replace:

A summary of treatment-emergent AEs with at least a 5% higher subject incidence in 1 treatment arm compared to the other will be presented by preferred term.

With:

For phase 3, a summary of treatment-emergent AEs with at least a 5% higher subject incidence in 1 treatment arm compared to the other will be presented by preferred term.

[Section: 10.5.4.1 Adverse Events](#), paragraph 6

Delete:

All races (if appropriate) with less than 5% of the total ~~randomized~~ subjects will be pooled together for summary purposes.

[Section: 10.5.4.2 Laboratory Test Results](#), paragraph 1

Replace:

Shift tables between the worst post-baseline and baseline grades for selected laboratory parameters will be provided. Plots or other summaries overtime will be presented for selected laboratory parameters including immunoglobulins, platelets, and liver parameters by treatment group for subjects in the Safety Analysis Set.

With:

Shift tables between the worst post-baseline and baseline grades for selected laboratory parameters will be provided. Plots or other summaries overtime will be presented for selected laboratory parameters including immunoglobulins, platelets, and liver parameters for subjects in the Safety Analysis Set. **The summary will be done by treatment group for phase 3.**

[Section: 10.5.4.3 Vital Signs](#), paragraph 1

Replace:

The number and percentage of subjects with abnormal changes in systolic blood pressure, diastolic blood pressure and heart rate will be summarized by treatment group for subjects in the Safety Analysis Set.

With:

The number and percentage of subjects with abnormal changes in systolic blood pressure, diastolic blood pressure and heart rate will be summarized for subjects in the Safety Analysis Set. **The summary will be done by treatment group for phase 3.**

[Section: 10.5.4.6 Exposure to Investigational Product](#), paragraph 1

Replace:

Descriptive statistics will be produced to describe the exposure to IP by treatment group for subjects in the Safety Analysis Set. For both treatment groups, the number of cycles of protocol-specified therapy administered will be summarized with an additional

Approved

breakdown of the number of cycles completed, discontinued, and re-started. In addition, the duration of therapy, the relative treatment duration, the cumulative dose, and the percent of intended dose will be summarized by cycle and overall for the treatment group and, if calculable, for the IC arm. The number and percent of subjects with dose modifications (eg, dose changes, dose interruptions) and reason for modification will be summarized for both treatment groups. For subjects receiving IC chemotherapy, the chemotherapy will be summarized.

With:

Descriptive statistics will be produced to describe the exposure to IP for subjects in the Safety Analysis Set. The number of cycles of protocol-specified therapy administered will be summarized with an additional breakdown of the number of cycles completed, discontinued, and re-started. In addition, the duration of therapy, the relative treatment duration, the cumulative dose, and the percent of intended dose will be summarized by cycle and overall. The number and percent of subjects with dose modifications (eg, dose changes, dose interruptions) and reason for modification will be summarized. **The summary will be done by treatment group for phase 3.**

[Section: 10.5.4.7 Exposure to Concomitant Medication](#), paragraph 1

Replace:

The number and proportion of subjects receiving concomitant medications from study day 1 through safety follow-up will be summarized by preferred term as coded by the World Health Organization Drug (WHODRUG) dictionary by treatment group in the Safety Analysis Set. In addition, the number and proportion of subjects receiving anticancer therapies (including HSCT conditioning regimens) during long term follow-up will be summarized by WHODRUG preferred term for each treatment group in the FAS.

With:

The number and proportion of subjects receiving concomitant medications from study day 1 through safety follow-up will be summarized by preferred term as coded by the World Health Organization Drug (WHODRUG) dictionary in the Safety Analysis Set. In addition, the number and proportion of subjects receiving anticancer therapies (including HSCT conditioning regimens) during long term follow-up will be summarized by WHODRUG preferred term in the FAS. **The summary will be done by treatment group for phase 3.**

Approved

Section: [12.4 Investigator Responsibilities for Data Collection](#), paragraph 1

Delete:

~~Amgen (or designee) will perform Self-Evident Corrections (SEC) to obvious data errors in the clinical trial database. SECs will be documented in the eCRF instructions available in the EDC system. Examples of obvious data errors that may be corrected by Amgen (or designee) include deletion of obvious duplicate data (ie, the same results sent twice with the same date with different visit, [eg, week 4 and early termination]) and updating a specific response if the confirming datum is provided in the “other, specify” field (eg, for race, reason for ending study).~~

Approved

OS	Overall Survival
PD	Progressive Disease
PD	Pharmacodynamic
PET-CT	Positron Emission Tomography-Computed Tomography
PFS	Progression Free Survival
PK	Pharmacokinetics
PMD	Progressive Metabolic Disease
PMR	Partial Metabolic Response
PR	Partial Response
R-IPI	Revised - International Prognostic Index
QOL	Quality of Life
QTc	Corrected QT Interval
R/R	Relapsed or Refractory
S1	First Salvage
S2	Second Salvage
SAP	Statistical Analysis Plan
SSAP	Supplemental Statistical Analysis Plan
WHODRUG	World Health Organization Drug

1. Introduction

The purpose of this Statistical Analysis Plan (SAP) is to provide details of the statistical analyses that have been outlined within the protocol Amendment 2 for the phase 2/3 blinatumomab study 20150292, dated **07 May 2019**. The scope of this plan includes the interim analyses, primary analysis and the final analysis that is planned and will be executed by the Global Biostatistics Science department unless otherwise specified. Pharmacokinetic, pharmacodynamic, exposure-response and biomarker analyses will be performed by Clinical Pharmacology Modeling and Simulation (CPMS) or biomarker group.

2. Objectives

2.1 Primary

To estimate the complete metabolic response (CMR) rate following blinatumomab monotherapy administered in the second salvage (S2) treatment of transplant-eligible subjects with relapsed or refractory (R/R) aggressive **B-cell Non-Hodgkin Lymphoma (B-NHL)** who have not achieved CMR following standard platinum-based first salvage (S1) chemotherapy

2.2 Secondary

- To evaluate additional efficacy parameters following blinatumomab treatment, including:
 - Duration of response (**DOR**)
 - Progression-free survival (PFS)
 - The rate of successful hematopoietic stem cell (HSC) mobilization
- To evaluate the safety of blinatumomab in the S2 setting
- To characterize the pharmacokinetic (PK) parameters of blinatumomab administered to subjects with R/R aggressive B-NHL

3. Study Overview

3.1 Study Design

This is an open label, multicenter trial testing blinatumomab monotherapy for the treatment of subjects with relapsed or refractory aggressive B-NHL not achieving CMR after standard platinum-based chemotherapy regimens administered as S1.

The primary endpoint for CMR rate will be determined during the first 12 weeks after initiation of blinatumomab.

Subjects with R/R aggressive B-NHL and considered by the investigator to be transplant eligible, but dependent upon the response to S2, will be enrolled after S1 chemotherapy

or if with progressive disease after 1 cycle of S1. In order to be eligible, subjects must undergo a restaging positron emission tomography-computed tomography (PET-CT) that is interpreted centrally as demonstrating less than CMR. To optimize subject recruitment and retention, pre-screening discussions may be conducted with potential subjects prior to the initiation of S1 chemotherapy. However, enrollment may not occur until the PET-CT results are **centrally reviewed and interpreted**.

Subjects who experience clinical evidence of progression following at least 1 cycle of S1 chemotherapy **may be eligible but will require pre-S1 imaging and post-S1 PET-CT** scan to confirm progression and to establish a new baseline for subsequent response assessment.

In the study, enrolled subjects will receive blinatumomab monotherapy.

[figure not shown]
Subjects in the study will receive a single 70-day cycle, **with a total of 56 days of blinatumomab continuous infusion of 7 days at 9 µg/day, 7 days at 28 µg/day, and 42 days at 112 µg/day**, followed by a treatment-free period of 14 days. Response will be assessed by central review of a PET-CT after this single cycle.

In the study, following response assessment, subjects may undergo HSCT mobilization and autologous HSCT or allogeneic HSCT. Subjects who demonstrate a response (PMR or CMR) to **blinatumomab** based on local assessment and who are not proceeding directly to autologous HSCT or allogeneic HSCT may receive an additional cycle of **blinatumomab** of maximum of 4-weeks. **Optional Cycle 2 blinatumomab dosing must start at least 2 weeks, but not more than 4 weeks, after the end of the previous cycle. Optional Cycle 2 blinatumomab consists of a 28 day cycle of blinatumomab continuous infusion administered 7 days at 9 µg/day, 7 days at 28 µg/day, and 14 days at 112 µg/day.**

Non-responding subjects (NMR or PMD/PD) are not eligible for retreatment with blinatumomab.

All subjects will have a safety follow-up no later than 30 (± 3) days after the last dose of blinatumomab.

3.1.1 Study Schema

CMR=complete metabolic response; HSCT=hematopoietic stem cell transplantation; PET-CT=positron emission tomography-computed tomography; PMR=partial metabolic response

a. Subjects with progressive metabolic disease may be eligible after 1 cycle of S1 chemotherapy

3.2 Sample Size

The sample size for the study is determined by a one-sample test of the rate of CMR during first 12 weeks after initiation of blinatumomab. With the one-sided type I error rate (α) set at 0.025, a null hypothesis response probability (π_0) of 15%, and an alternative response probability (π_1) of 40%, a sample size of 36 subjects will provide 90% power to reject the null hypothesis that the response probability is no more than 15%.

4. Study Endpoints and Covariates

4.1 Study Endpoints

4.1.1 Primary Endpoint

- CMR: CMR is determined by central radiographic assessment of PET-CT scans **ie, central review** using the Lugano Classification. Subject's CMR status is determined by whether the subject achieves CMR during the first **12 weeks** after initiation of blinatumomab.

4.1.2 Other Secondary Endpoints

- Objective response (OR; including CMR and PMR)
- PFS
- Overall survival**
- Duration of CMR for subjects who achieved CMR **per investigator's review** during the first **12 weeks** since starting blinatumomab
- Duration of response (DOR) for subjects who achieved response **per investigator's review during the first 12 weeks since starting blinatumomab**
- Successful mobilization rate (**defined as CD34+ cell 2x10⁶/kg**)
- Autologous HSCT (autoHSCT) rate among subjects with post –blinatumomab CMR+PMR **per investigator's review**
- Allogeneic HSCT (alloHSCT) rate among subjects with post-blinatumomab CMR+PMR **per investigator's review**
- 100-day non-relapse mortality (NRM) after HSCT
- Blinatumomab concentration steady state, clearance, and half life

4.1.3 Safety Endpoint

- Incidence and severity of adverse events

4.1.4 Exploratory Endpoints

- Pharmacodynamics, including descriptive analysis of quantitative and qualitative features of lymphocyte populations and serum or plasma concentrations of cytokines
- Response rates and duration according to COO designation and c-myc and bcl-2 rearrangement and over expression, R-IPI, Secondary IPI, NCCN IPI, as determined from pretreatment specimens

- Quantitative analysis of CT-DNA as determined by **analysis of tumor-associated mutations in CF CT-DNA** from plasma collected at various timepoints before, during, and after treatment

4.2 Exploratory

- To characterize the pharmacodynamic effects of blinatumomab administered in temporal proximity to various S1 regimens
- To evaluate the response rate according to disease-specific features, such as cell-of-origin (COO), c-myc and bcl-2 rearrangements **and over expression, Revised International Prognostic Index (R-IPI), Secondary International Prognostic Index (IPI), National Comprehensive Cancer Network International Prognostic Index (NCCN IPI), first response status before blinatumomab, duration of first remission before blinatumomab**
- To evaluate the frequency of **tumor-associated mutations in cell-free (CF) circulating tumor (CT- DNA)** among subjects at various time points during and after salvage treatment
- To determine the incidence of anti-blinatumomab antibody formation

5. Hypotheses and/or Estimations

The complete metabolic response (CMR) rate during the first 12 weeks since starting blinatumomab will be estimated for blinatumomab monotherapy administered in the second salvage (S2) treatment of transplant-eligible subjects with relapsed or refractory (R/R) aggressive B-NHL who have not achieved CMR.

6. Definitions

6.1 General Definitions

Age at Screening

Subject age at screening will be collected in years in the clinical database.

Baseline

For the analysis of all endpoints, baseline will be defined as the value measured on day 1 of the first cycle of blinatumomab. The protocol specifies that procedures and labs on day 1 should be completed before the initiation of protocol-specified therapy which will be the assumption in the analysis unless the time of the assessment is recorded. If a day 1 value is not available, the most recent value before the day of the start of blinatumomab may be used.

Complete Cycle

If a subject had blinatumomab exposure of $\geq 90\%$ of planned duration of a cycle, he/she is considered to have completed the given cycle.

Cumulative Dose of Blinatumomab

Blinatumomab: The cumulative dose in μg is defined as the following with summation over infusions:

$$\sum (\text{duration of infusion (days)} \text{ for each dose received} \times \text{dose received} [\mu\text{g}])$$

Cumulative dose will be calculated within a cycle and across all cycles.

Death Date

For subjects who die during the study, the death date will be recorded on the event, end of study and/or survival status CRF. The earliest date will be used if the dates are inconsistent among these CRF pages. For deaths collected after a subject has ended study (eg, through public records), the death date will be recorded on the CRF long term follow-up page.

Duration of Blinatumomab

Blinatumomab: For each infusion episode within a cycle, the duration of exposure will be calculated by subtracting the start date and time from the stop date and time. If either a start or stop time is missing, only the date portion will be used in calculating the duration of a specific infusion. For each cycle, the duration will be last date minus first date plus 1 of infusion. For the entire study, the duration will be the sum of the durations across cycles. The duration will be rounded to the nearest day.

Investigational Product

Investigational product refers to blinatumomab.

Last Dose Date of Blinatumomab Administration

This is the stop date of the last infusion of blinatumomab administered reported on investigational product administration CRF.

Percent of Intended Dose of Blinatumomab

For a first cycle, the percent of intended dose of blinatumomab will be the cumulative dose, in micrograms, in that cycle divided by the planned cumulative dose for that cycle.

For the first cycle, the planned cumulative dose will be $(9 \mu\text{g} \times 7 \text{ days}) + (28 \mu\text{g} \times 7 \text{ days}) + (112 \mu\text{g} \times 42 \text{ days}) = 4963 \mu\text{g}$. For 2nd cycles, the planned cumulative dose will be $(9 \mu\text{g} \times 7 \text{ days}) + (28 \mu\text{g} \times 7 \text{ days}) + (112 \mu\text{g} \times 14 \text{ days}) = 1827 \mu\text{g}$. For the entire study, the percent of intended dose of blinatumomab will be the sum of the cumulative doses

across cycles divided by the sum of the planned cumulative doses across the cycles started.

Prior Salvage Regimens

Prior salvage regimens are those medications recorded on the prior anti-cancer therapies CRF where the line of therapy field indicates 1st salvage chemotherapy.

Relative Treatment Duration of Blinatumomab

For 1st cycle, the relative treatment duration will be duration of blinatumomab infusion for that cycle divided by 56 days, the planned duration of infusion. For 2nd cycle (if administered), planned duration of infusion will be 28 days.

Study Day

Study Day 1 is defined as:

The day of the first cycle of blinatumomab.

And Study Day is defined as:

Pre study day 1: study day= (date – date of study day 1)

On and after study day 1: study day= (date - date of study day 1) + 1

Study-level End of Study Date:

The final analysis will occur when all subjects in phase 2 complete long term follow-up.

Subject-level End of Study (EOS) Date

End of study for each subject is defined as the date the subject last completed a protocol-specified procedure. The date will be recorded on the End of Study CRF page.

Treatment-emergent Adverse Event (TEAE)

Treatment emergent adverse event refers to an adverse event that starts after the first dose of blinatumomab up to and including 30 days after the end of blinatumomab. It is indicated by a flag whether an event started before first dose of blinatumomab on the Event CRF page. This reporting window also applies to treatment-emergent serious adverse events (SAEs).

Treatment-emergent Disease-related Event

Treatment emergent disease-related event refers to a disease-related event that starts on or after the first dose of blinatumomab up to and including 30 days after the end of

blinatumomab. It is indicated by a flag whether an event started before first dose of blinatumomab on the Event CRF page. This reporting window also applies to treatment-emergent serious disease-related events (SDREs).

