6.2.2.2 Infusion Interruption/Dose Modifications due to Adverse Events

Infusion interruptions and dose modifications of blinatumomab due to adverse events are detailed in [Table 2](#). Infusions will be resumed according to instructions in [Table 2](#) in order to complete the full treatment cycle, excluding the duration of treatment interruption (56 days blinatumomab in cycle 1, 28 days blinatumomab in optional cycle 2).

Table 2. Infusion Interruption/Dose Modifications of Blinatumomab due to Adverse Events

Toxicity	Grade	Instructions for Treatment Interruption and Restart
Cytokine Release Syndrome	3	
 • Interrupt blinatumomab until the event improves to grade ≤ 1 and administer corticosteroids (refer to Table 3) • Restart no less than 72 hours after the initial observation of the grade 3 event at the following dose levels: 
 ○ If event occurred at 112 $\mu\text{g}/\text{day}$, resume at 28 $\mu\text{g}/\text{day}$ ○ If event occurred at 9 or 28 $\mu\text{g}/\text{day}$, resume at 9 $\mu\text{g}/\text{day}$ • Escalate up 1 dose level after 7 days if toxicity does not reoccur. Increase dose stepwise at 7-day intervals to target dose of 112 $\mu\text{g}/\text{day}$ if toxicity does not reoccur. • Permanently discontinue if: 
 ○ Initial grade 3 CRS does not improve to grade ≤ 1 within 7 days, OR ○ Grade 3 CRS reoccurs at the lower dose level within 7 days of reinitiation OR ○ Grade 3 CRS reoccurs at a dose of 9 $\mu\text{g}/\text{day}$ without prior step-dose escalation
	4	
 • Permanently discontinue blinatumomab

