Neurologic Events	3	
 • Interrupt blinatumomab until the event improves to grade ≤ 1 and administer corticosteroids (refer to Table 3) • Restart no less than 72 hours after the initial observation of the grade 3 event at the following dose levels: 
 ○ If event occurred at 112 $\mu\text{g}/\text{day}$, resume at 28 $\mu\text{g}/\text{day}$ ○ If event occurred at 28 $\mu\text{g}/\text{day}$, resume at 9 $\mu\text{g}/\text{day}$ • Escalate up 1 dose level after 7 days if toxicity does not reoccur. Increase dose stepwise at 7-day intervals to target dose of 112 $\mu\text{g}/\text{day}$ if toxicity does not reoccur. • Permanently discontinue if: 
 ○ Initial grade 3 neurologic event occurred at 9 $\mu\text{g}/\text{day}$, ○ Initial grade 3 neurologic event does not improve to grade ≤ 1 within 7 days, OR ○ Grade 3 neurologic event reoccurs at the lower dose level within 7 days of re-initiation
	4	
 • Permanently discontinue blinatumomab
	4	
 • Permanently discontinue blinatumomab

Approved

ALP=alkaline phosphatase; ALT=alanine aminotransferase; AST=aspartate aminotransferase; CRS=cytokine release syndrome; INR=international normalized ratio; MRI=magnetic resonance imaging; RUQ=right upper quadrant; TBL=total bilirubin; ULN=upper limit of normal
 * Obtain brain MRI and perform cerebro spinal fluid (CSF) analysis, if there are no contraindications

Table 2. Infusion Interruption/Dose Modifications of Blinatumomab due to Adverse Events

Toxicity	Grade	Instructions for Treatment Interruption and Restart
Seizure*		
 Interrupt blinatumomab, administer corticosteroids (refer to Table 3) and antiseizure medication per local practice For restart, refer to grade 3 neurologic events above for dose level rules for re-instituting infusion Do not re-initiate blinatumomab until 7 days after the last seizure and after therapeutic levels of antiseizure medication are likely to have been achieved Permanently discontinue if a second seizure occurs with re-initiation of blinatumomab at any dose

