10.6.7 Exposure to Investigational Product

Descriptive statistics will be produced to describe the exposure to blinatumomab in the Safety Analysis Set. The number of cycles administered will be summarized with an additional breakdown of the number of cycles completed and discontinued. In addition, the duration of therapy, the relative treatment duration, the cumulative dose, and the percent of intended dose will be summarized by cycle and overall. The number and percent of subjects with dose modifications (eg, dose changes, dose interruptions) and reason for modification will be summarized.

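### SAP 6.1 does not name the numerator of relative treatment duration; its only cycle-level duration is a calendar span that counts interruptions, while the 56- or 28-day denominator excludes them

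*SAP*

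**What the plan says.** SAP 6.1 defines duration of blinatumomab at three levels.

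- **Episode:** "the duration of exposure will be calculated by subtracting the start date and time from the stop date and time".
- **Cycle:** "For each cycle, the duration will be last date minus first date plus 1 of infusion".
- **Study:** "For the entire study, the duration will be the sum of the durations across cycles".

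No rule adds episodes up within a cycle or subtracts the time between them.

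A later entry in the same section defines the ratio for cycle 1: "the relative treatment duration will be duration of blinatumomab infusion for that cycle divided by 56 days, the planned duration of infusion". For cycle 2 the divisor is 28 days. SAP 10.6.7 plans to report the result: "the duration of therapy, the relative treatment duration, the cumulative dose, and the percent of intended dose will be summarized by cycle and overall".

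Protocol 6.2.2.2 fixes what the 56 and 28 days are. The stated aim of resuming after an interruption is this: "complete the full treatment cycle, excluding the duration of treatment interruption (56 days blinatumomab in cycle 1, 28 days blinatumomab in optional cycle 2". Its Table 2 makes interruptions of several days foreseeable. After a grade 3 event the instruction is "Restart no less than 72 hours after the initial observation of the grade 3 event"; after a seizure it is "Do not re-initiate blinatumomab until 7 days after the last seizure".

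**The concern.** Relative treatment duration should show how much of the planned infusion time a subject received. If the numerator is the first-to-last span, interruption days that precede a resumption enter the numerator but not the denominator. The ratio then rises with the length of the interruption. It can exceed 100% in a subject who received exactly the planned infusion days, and it can read about 100% in one who missed some of them.

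What is at stake is the reading of one exposure table. The CMR analysis, the analysis sets, the adverse event tables, cumulative dose and percent of intended dose do not use this ratio.

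**Working it through.** **Inputs.** Planned infusion days P come from the dosing schedule (SAP 3.1, SAP 6.1, Protocol 6.2.1). The SAP's own figures reproduce:

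- Cycle 1: 7 + 7 + 42 = 56 days; 9×7 + 28×7 + 112×42 = 63 + 196 + 4704 = 4963 µg.
- Cycle 2: 7 + 7 + 14 = 28 days; 63 + 196 + 1568 = 1827 µg.

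**Assumptions.** There is one interruption of g whole days, infusion resumes in the same cycle, d days are infused in total, and start and stop fall at the same clock time. The gap lengths of 3 and 7 days are illustrative. They are suggested by the restart rules in Table 2 but are not observed values. The 72 hours there run from first observation of the event, not from stopping the pump, so an actual gap could be somewhat shorter than 3 days.

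**Formulas.**

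- Literal cycle rule: (last date − first date + 1)/P = (d + g + 1)/P.
- Summed episodes: d/P.
- Difference: (g + 1)/P, of which g/P comes from the interruption and 1/P from the plus 1.

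**Results.**

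| Cycle | Days infused | Gap (days) | Literal span rule | Summed episodes |
|---|---|---|---|---|
| 1 | 56 | 0 | 57/56 = 101.8% | 100.0% |
| 1 | 56 | 3 | 60/56 = 107.1% | 100.0% |
| 1 | 56 | 7 | 64/56 = 114.3% | 100.0% |
| 1 | 49 | 7 | 57/56 = 101.8% | 87.5% |
| 2 | 28 | 0 | 29/28 = 103.6% | 100.0% |
| 2 | 28 | 7 | 36/28 = 128.6% | 100.0% |

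The gap alone contributes 3/56 = 5.4 or 7/56 = 12.5 percentage points in cycle 1, and 7/28 = 25.0 points in cycle 2. The plus 1 is a separate one-day convention worth 1/56 = 1.8 or 1/28 = 3.6 points.

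The first and fourth rows are identical under the span rule: an uninterrupted full cycle and a cycle short by 7 infusion days both read 101.8%.

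If a subject stops for good at the first interruption, the last infusion date precedes the gap and g = 0.

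**The case against.** The strongest reply is that the SAP means summed episodes. The entry for the ratio speaks of the duration of infusion for the cycle and sets it against a planned duration of infusion, which reads naturally as like over like. The cumulative dose formula in the same section uses infusion days in that sense. The duration entry also calls for rounding to the nearest day, which does nothing to a difference of dates but does matter for date-and-time durations. This makes summed episodes a plausible intent. It does not settle the matter: the rounding may apply to episodes only, and the one cycle-level duration that the SAP defines is the span. A programmer working from 6.1 could defensibly use either.

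The second reply is that little is lost, and this largely stands. SAP 10.6.7 reports cumulative dose, percent of intended dose and interruptions with reasons beside the ratio. Cumulative dose is summed over infusions and so leaves out gaps. If the 49-day subject missed 7 days at 112 µg/day with no other dose change, percent of intended dose would be (4963 − 784)/4963 = 84.2%, and the shortfall would show there. The 49-day case also needs a further early stop, because the protocol has interrupted subjects resume in order to complete the cycle.

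Third, a first-to-last span is a legitimate measure of time on therapy when labelled as such. The mismatch is only in the ratio.

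**Conclusion.** The point holds as a conditional and minor one. Followed literally, SAP 6.1 overstates relative treatment duration by about g/56 or g/28 after a resumed multi-day interruption, plus the small constant from the plus 1. If summed episodes are meant, the defect is only that the SAP does not say so. The sizes rest on the assumed gap lengths, whole-day gaps and equal clock times.

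A reader might infer more than the documents support:

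- **That the reported exposure will be materially inflated.** No interruption frequency is given for this trial, so no shift in a mean or median can be claimed.
- **That a value above 100% reveals an interruption.** The plus 1 alone gives 101.8% or 103.6% with no gap.
- **That missed treatment would be concealed.** Percent of intended dose and the interruption summary stand beside the ratio.
- **That the 90% rule for a completed cycle, or cycles restarted from day 1, is wrong too.** The SAP does not say which duration the 90% rule uses, and the arithmetic here does not cover restarted cycles.
- **That efficacy or safety conclusions are affected.** They do not use this quantity.

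**What to change.** In SAP 6.1, under relative treatment duration, state that the numerator is the sum of the infusion-episode durations within the cycle, each taken as stop minus start date and time, over 56 planned infusion days in cycle 1 or 28 in cycle 2. If the first-to-last span is kept as duration of therapy, label it there and in the table as calendar time including interruptions.

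With that numerator, 56 of 56 and 28 of 28 infused days read 100.0%, and 49 of 56 reads 87.5%, whatever the gap. One small imprecision remains: where a start or stop time is missing, the SAP falls back on dates, which leaves a rounding error in that episode.

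The cost is one sentence and one label. Episode durations are already derived, so no new data are needed, and no treatment rule changes.
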